8.1. Statistical methods

8.1.1. Analysis of continuous data

Summary statistics (number of patients, mean, standard deviation, median, maximum, and minimum) will be calculated.

If a test is performed for comparison of before and after administration of Lyrica, a paired t-test will be used. If changes before and after administration of Lyrica (change = value after administration - value before administration) are compared between subgroups, the effect of the factor will be tested (P-value will be calculated) with an analysis of covariance model using the factor to be evaluated as a factor and the value before administration as a covariate, and the least squares mean, standard error, and 95% confidence interval of change will be calculated for each subgroup.

8.1.2. Analysis of categorical data

Frequency (e.g., number of patients) and its proportion (composition ratio) of each category will be calculated.

8.1.3. Analysis of binary data

Frequency and its proportion will be calculated. If the confidence interval of proportion is calculated, a 2-sided 95% confidence interval (exact method) will be calculated.

If the proportion is compared between subgroups, Fisher’s exact test and Cochran-Armitage test (exact method) will be performed for the relationships with nominal scale data and ordinal scale data, respectively, and the risk ratio and risk difference with their 95% confidence intervals will be calculated.

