## 3 Target sample size

The target sample size is 3400 patients with neuropathic pain in total, including 3000 patients with peripheral neuropathic pain (1000 patients with post herpetic neuralgia, if possible, and 2000 patients with peripheral neuropathic pain of the types other than post herpetic neuralgia), and 400 patients with central neuropathic pain (300 patients with post-stroke pain, if possible, and other patients with pain following traumatic spinal cord injury and pain due to Parkinson's disease). For peripheral neuropathic pain, approximately 100 each of patients should be accumulated, if possible, for trigeminal neuralgia, peripheral entrapment neuropathy, iatrogenic neuropathy, neuropathy due to tumor-induced nerve compression or infiltration, posttraumatic pain, and chronic cauda equina syndrome.

[Rationale]

The target sample size of 3400 patients with neuropathic pain is expected to have a 97% probability to detect adverse reactions occurring at the incidence of 0.1% or higher in at least 1 patient. Of the adverse reactions included in the major investigation items, vision-related events are anticipated to develop at the lowest incidence during the survey. In clinical studies of the product conducted in Japan and overseas, the lower bound of the 95% confidence interval for the incidence of this adverse reaction was 6.70% (incidence 7.40%, 380/5134 patients). If this adverse reaction develops at the same incidence as in these clinical studies, this reaction is expected to occur in 227 or more of 3400 patients. Since the safety and efficacy of the product should be evaluated in patients with each type of neuropathic pain, enrollment of the following number of patients will be ensured; approximately 100 patients each, if possible, for trigeminal neuralgia, peripheral entrapment neuropathy, iatrogenic neuropathy, neuropathy due to tumor-induced nerve compression or infiltration, posttraumatic pain, and chronic cauda equina syndrome, approximately 300 patients for post-stroke pain, and a certain number of patients for pain following traumatic spinal cord injury and pain due to Parkinson's disease.

This sample size will also allow for adequate evaluation of the characteristics of other adverse reactions included in the major investigation items. The characteristics to be evaluated include time of onset and duration of adverse reactions, and these were also investigated in the clinical studies.

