The target sample size is 3400 patients with neuropathic pain in total, including 3000 patients with peripheral neuropathic pain (1000 patients with postherpetic neuralgia, if possible, and 2000 patients with peripheral neuropathic pain of the types other than postherpetic neuralgia), and 400 patients with central neuropathic pain (300 patients with post-stroke pain, if possible, and other patients with pain following traumatic spinal cord injury and pain due to Parkinson's disease). For peripheral neuropathic pain, approximately 100 each of patients should be accumulated, if possible, for trigeminal neuralgia, peripheral entrapment neuropathy, iatrogenic neuropathy, neuropathy due to tumor-induced nerve compression or infiltration, posttraumatic pain, and chronic cauda equina syndrome.

The target sample size of 3400 patients with neuropathic pain is expected to have a 97% probability to detect adverse reactions occurring at the incidence of 0.1% or higher in at least 1 patient. Of the adverse reactions included in the major investigation items, vision-related events are anticipated to develop at the lowest incidence during the survey. In

clinical studies of Lyrica conducted in Japan and overseas, the lower bound of the 95% confidence interval for the incidence of this adverse reaction was 6.70% (incidence 7.40%, 380/5134 patients). If this adverse reaction develops at the same incidence as in these clinical studies, this reaction is expected to occur in 227 or more of 3400 patients. Since the safety and efficacy of Lyrica should be evaluated in patients with each type of neuropathic pain, enrollment of the following number of patients will be ensured; approximately 100 patients each, if possible, for trigeminal neuralgia, peripheral entrapment neuropathy, iatrogenic neuropathy, neuropathy due to tumor-induced nerve compression or infiltration, posttraumatic pain, and chronic cauda equina syndrome, approximately 300 patients for post-stroke pain, and a certain number of patients for pain following traumatic spinal cord injury and pain due to Parkinson's disease.

This sample size will also allow for adequate evaluation of the characteristics of other adverse reactions included in the major investigation items. The characteristics to be evaluated include time of onset and duration of adverse reactions, and these were also investigated in the clinical studies.

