4.1. Statistical hypothesis

Because this survey is not a confirmatory investigation, the testing should be considered as exploratory in nature. Unless otherwise specified, the 2-sided testing is performed with a significance level of 5%.

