8.2. Statistical analyses

8.2.1. General description of patients

- **Number of institutions and patients to be surveyed by establishment category**

Number of institutions and patients with their proportion by establishment category are to be calculated for the patients whose survey forms collected:

- National, public and private university hospitals
- National hospitals established by the Ministry of Health, Labour and Welfare
- Prefectural and municipal hospitals
- Public organizations
- Hospitals established by corporations and individuals not described above
- General practitioners and clinics

Additionally, mean, minimum, and maximum of the number of patients per institution will be calculated.

- **Patient disposition**

For registered patients, number of registered patients, patients whose survey form was collected, and patients included in the safety analysis set and efficacy analysis set will be tabulated. Also, number of patients whose survey form was not collected, patients excluded from safety analysis and efficacy analysis and number of patients by reason for exclusion will be tabulated.

- **Listing of discontinuations and dropouts**

Number and proportion of discontinued patients will be tabulated by timing of discontinuation (≤ 4 weeks, >4 to ≤ 13 weeks, and >13 weeks) in the safety analysis set. In addition, number and proportion of patients will be tabulated by reason for discontinuation.

- **Listing of excluded patients**

Listings of patients excluded from safety analysis and efficacy analysis, and reasons for exclusion will be prepared. In addition, name of disease of patients excluded from efficacy analysis because of non-target disease of the survey will be tabulated by PT.

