8.2.4. Efficacy analysis

8.2.4.1. Clinical efficacy

Response rate (number of effective patients / [number of effective patients + number of ineffective patients]) and its 95% confidence interval will be calculated.

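### The exact 95% interval for the response rate ignores institutions and is too narrow if outcomes correlate within them; factor tests over-reject only for factors concentrated by institution

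*SAP*

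**What the plan says.** SAP 8.1.3 governs binary outcomes. For proportions: "If the confidence interval of proportion is calculated, a 2-sided 95% confidence interval (exact method) will be calculated". For comparisons between subgroups it names Fisher's exact test and then the trend test, "Cochran-Armitage test (exact method) will be performed for the relationships with nominal scale data and ordinal scale data", in that order, together with risk ratios and risk differences and their 95% intervals. None of these is stratified or adjusted for institution.

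The one proportion for which an interval is expressly planned is the response rate in SAP 8.2.4.1: the rate "and its 95% confidence interval will be calculated". Risk ratios and differences for adverse reactions get intervals in SAP 8.2.3.4. For overall adverse reactions and the major investigation items, SAP 8.2.3.1 plans only numbers and proportions.

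SAP 8.2.1 shows the grouping. Institutions are classified by type, from university hospitals to clinics, and "mean, minimum, and maximum of the number of patients per institution will be calculated". This is description only: nowhere in the protocol or SAP does institution enter an analysis as cluster, stratum or random effect. SAP 6.4 identifies no covariates.

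On who judges: Protocol 6.7 asks for an effective/ineffective judgment without naming the rater, but Protocol 6 has the investigator fill in the survey form. Causal relationship is recorded under Protocol 6.8, and SAP 6.1 counts an event as an adverse reaction if the investigator or the sponsor considers it related.

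**The concern.** Patients seen at one institution are likely to share raters, reporting habits and prescribing habits. If so, their outcomes are positively correlated, and 3400 patients carry less information than 3400 independent ones. An exact binomial interval then claims more precision than the data hold.

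The response rate is the primary efficacy item (Protocol 7.2.2), so its interval is likely to be reported and read. Finding factors that affect safety and efficacy is a stated objective (SAP 2.2). A significant factor triggers breakdowns by SOC and PT (SAP 8.2.3.4) and, as necessary, demographic tables (SAP 8.2.4.6). If a factor follows institutional habit, a difference between institutions can appear as a patient risk factor.

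**Working it through.** **The plan's own figures.** The target is stated as: "The target sample size is 3400 patients with neuropathic pain in total". The SAP says this is "expected to have a 97% probability to detect adverse reactions occurring at the incidence of 0.1% or higher in at least 1 patient". Check: 1 − (1 − 0.001)^3400 = 0.967, which agrees. The exact lower bound for 380/5134 is 6.70%, and 3400 × 0.067 = 227.8, which matches the stated 227 or more. Clustering does not change that expected count, because an expectation does not depend on correlation.

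**Assumed inputs.** The documents give neither m (patients per institution) nor ICC (intra-institution correlation). I take m = 5 to 20 and ICC = 0.01 to 0.10, with institutions of equal size. A 75% response rate in 3400 patients is used only to express half-widths. The real denominator is smaller, because SAP 8.2.4.1 counts only patients judged effective or ineffective.

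**Response-rate interval.** Design effect DE = 1 + (m − 1) × ICC. The half-width should grow by about √DE. Approximate coverage of the nominal interval = 2Φ(1.96/√DE) − 1. The unadjusted exact half-width is 1.47 points; adjusted half-widths use the exact method at 3400/DE patients.

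| m | ICC | DE | √DE | Coverage | Adjusted half-width (points) |
|---|---|---|---|---|---|
| 5 | 0.01 | 1.04 | 1.02 | 94.5% | 1.50 |
| 5 | 0.05 | 1.20 | 1.10 | 92.6% | 1.61 |
| 10 | 0.05 | 1.45 | 1.20 | 89.6% | 1.77 |
| 10 | 0.10 | 1.90 | 1.38 | 84.5% | 2.03 |
| 20 | 0.10 | 2.90 | 1.70 | 75.0% | 2.52 |

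Middle row: 1 + 9 × 0.05 = 1.45; √1.45 = 1.204; 1.96/1.204 = 1.628; 2Φ(1.628) − 1 = 0.896.

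**Factor tests.** What matters here is the outcome ICC multiplied by the factor's own concentration within institutions: DE_factor = 1 + (m − 1) × ICC_outcome × ICC_factor, and type I error = 2 × (1 − Φ(1.96/√DE_factor)). I set this beside simulated rejection rates of the 5% Fisher test with no true effect (beta-binomial institutions, 25% outcome rate, 1000 runs per cell). Each cell shows simulation / formula.

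| m | Outcome ICC | Factor varies freely (ICC 0) | Partly concentrated (ICC 0.2) | Fully shared (ICC 1) |
|---|---|---|---|---|
| 5 | 0.05 | 4.7% / 5.0% | 5.9% / 5.5% | 7.2% / 7.4% |
| 10 | 0.05 | 5.1% / 5.0% | 6.4% / 6.0% | 11.5% / 10.4% |
| 10 | 0.10 | 5.3% / 5.0% | 6.2% / 7.1% | 15.7% / 15.5% |
| 20 | 0.10 | 4.9% / 5.0% | 8.9% / 9.5% | 22.1% / 25.0% |

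Simulation error near 5% is about √(0.05 × 0.95/1000) = 0.7 points (one standard error). Over all settings tried, freely varying factors gave about 4% to 7%, with no systematic excess. The trend test, simulated in its asymptotic form with 2000 runs per cell, behaved alike: 4% to 6% for freely varying factors and 7% to 26% for fully shared ones (outcome ICC 0.05 to 0.10).

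**The case against.** The strongest reply is that the size rests wholly on assumed inputs and the consequence is small. At m = 5 and ICC 0.01 the half-width moves from 1.47 to 1.50 points, which nobody would notice. SAP 4.1 calls all testing exploratory, SAP 4.2 sets no decision rule, and no comparator or threshold exists that a wider interval could cross. A false-positive factor leads to extra descriptive tables, and several breakdowns (by target disease, initial dose, elderly, pediatric, renal and hepatic patients) are produced whatever the tests show. All of this stands, and it keeps the point minor. It does not make the interval correct.

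A reader might infer more than the documents support:

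- **That the factor tests over-reject in general.** They do not. Every factor in SAP 5.4 is recorded per patient, and one that varies freely within institutions keeps about 5%. The excess is confined to factors concentrated by institution. Inpatient status, target disease, starting dose and concomitant drugs are possible examples, but nothing in the documents says how they are distributed.
- **That adverse-reaction incidences carry intervals that are too narrow.** SAP 8.1.3 is conditional, and SAP 8.2.3.1 plans no interval for overall incidence or the major investigation items.
- **That patients of one institution share a single judge.** Protocol 5.3 issues access to each investigator, and an institution may have several. The sponsor may also classify causality.
- **That the argument carries over to the analysis of covariance in SAP 8.1.1.** It is applied to pain scores, which patients rate themselves, so shared judgment at the site does not reach them.

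Replacing every test by a logit GEE would also be a poor trade: it gives odds ratios rather than the planned risk ratios and differences, and it may be unstable in sparse levels such as children or doses above 600 mg.

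**Conclusion.** The point holds in a limited form. SAP 8.1.3 treats patients as independent although they are nested in institutions, and any positive within-institution correlation makes the response-rate interval too narrow. Over the assumed range it should be 1.02 to 1.70 times wider. Coverage of the nominal 95% interval runs from about 94.5% to 75%, with about 90% in the middle case. Which case applies cannot be known until the observed ICC is reported. The figures assume equal institution sizes; for the same mean, unequal sizes would raise the design effect.

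For the factor comparisons the concern is confined to factors concentrated by institution: 7% to 22% in the simulated Fisher cells shown for a fully shared factor, and about 6% to 9% for a partly concentrated one. Severity is minor, because testing is exploratory and nothing is decided by a rule.

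**What to change.** - In SAP 8.1.3 and 8.2.4.1, compute the 95% interval for the response rate with institution as the cluster, by robust variance or GEE.
- In SAP 8.2.1, report the observed intra-institution correlation beside the patients-per-institution table.
- For SAP 5.4 factors with enough patients per level, add institution-robust risk ratios and risk differences as a sensitivity analysis, using a log or identity link or standardization from a logit model. Read a factor as a patient risk factor only if the association persists there.
- Keep the exact tests and intervals for sparse levels and rare PTs.

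The cost is some SAP wording, one additional model and somewhat wider intervals. No new data are needed, since the tabulation in SAP 8.2.1 already requires each patient's institution. If the observed correlation is near zero, the exact interval is supported by the data.

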8.2. Statistical analyses

8.2.1. General description of patients

- **Number of institutions and patients to be surveyed by establishment category**

Number of institutions and patients with their proportion by establishment category are to be calculated for the patients whose survey forms collected:

- National, public and private university hospitals
- National hospitals established by the Ministry of Health, Labour and Welfare
- Prefectural and municipal hospitals
- Public organizations
- Hospitals established by corporations and individuals not described above
- General practitioners and clinics

Additionally, mean, minimum, and maximum of the number of patients per institution will be calculated.

- **Patient disposition**

For registered patients, number of registered patients, patients whose survey form was collected, and patients included in the safety analysis set and efficacy analysis set will be tabulated. Also, number of patients whose survey form was not collected, patients excluded from safety analysis and efficacy analysis and number of patients by reason for exclusion will be tabulated.

- **Listing of discontinuations and dropouts**

Number and proportion of discontinued patients will be tabulated by timing of discontinuation (≤ 4 weeks, >4 to ≤ 13 weeks, and >13 weeks) in the safety analysis set. In addition, number and proportion of patients will be tabulated by reason for discontinuation.

- **Listing of excluded patients**

Listings of patients excluded from safety analysis and efficacy analysis, and reasons for exclusion will be prepared. In addition, name of disease of patients excluded from efficacy analysis because of non-target disease of the survey will be tabulated by PT.

8.2.2. Patient demographics and treatment history

- **Patient demographics**

The following patient demographics will be tabulated in the safety analysis set and efficacy analysis set in accordance with Section 8.1.

- Sex [male, female]

- Age at the start of treatment (continuous data)
- Age category at the start of treatment [<15 years, ≥ 15 to <65 years, ≥ 65 years]
- Age category at the start of treatment [<65 years, ≥ 65 to <70 years, ≥ 70 to <75 years, ≥ 75 to <80 years, ≥ 80 to <85 years, ≥ 85 years]
- Inpatient/outpatient status at the initial prescription [inpatient, outpatient]
- Height at the start of treatment (by sex) (continuous data)
- Body weight at the start of treatment (by sex) (continuous data)
- Body weight category at the start of treatment (by sex) [<40 kg, ≥ 40 to <50 kg, ≥ 50 to <60 kg, ≥ 60 kg]
- Name of target disease (i.e., diagnosis of neuropathic pain) [by disease name]
- Duration of target disease (i.e., diagnosis of neuropathic pain) (continuous data)
- Severity of target disease (i.e., diagnosis of neuropathic pain) [mild, moderate, severe]
- Pain score (continuous data)
- Name of underlying disease (i.e., primary disease of nerve damage that cause neuropathic pain) [by disease name]
- Hepatic impairment [no, yes (mild, moderate, severe)]
- Renal impairment [no, yes (mild, moderate, severe)]
- Hemodialysis [no, yes]
- Creatinine clearance category [<15 mL/min, ≥ 15 to <30 mL/min, ≥ 30 to <60 mL/min, ≥ 60 mL/min]
- Hyperalgesia [no, yes]
- Past medical history [no, yes]
- Complications [no, yes]

The following number and proportion of patients will be tabulated by SOC and PT in the safety analysis set.

- Breakdown of underlying disease
- Breakdown of past medical history
- Breakdown of complications

The following number and proportion of patients will be tabulated in the safety analysis set and efficacy analysis set.

- Presence or absence and breakdown of concomitant medications
- Presence or absence and breakdown of concomitant non-medication therapies
- Presence or absence and breakdown of prior medications

If patient demographics are tabulated by subgroup based on the initial dose specified in Section 5.4, the following will be tabulated in the safety analysis set and efficacy analysis set in accordance with Section 8.1.

- Age at the start of treatment (continuous data)

- Age category at the start of treatment [<15 years, ≥ 15 to <65 years, ≥ 65 years]
- Age category at the start of treatment [<65 years, ≥ 65 to <70 years, ≥ 70 to <75 years, ≥ 75 to <80 years, ≥ 80 to <85 years, ≥ 85 years]
- Body weight at the start of treatment (by sex) (continuous data)
- Body weight category at the start of treatment (by sex) [<40 kg, ≥ 40 to <50 kg, ≥ 50 to <60 kg, ≥ 60 to <70 kg, ≥ 70 to <80 kg, ≥ 80 to <90 kg, ≥ 90 to <100 kg, ≥ 100 kg]
- Duration of target disease (i.e., diagnosis of neuropathic pain) (continuous data)
- Severity of target disease (i.e., diagnosis of neuropathic pain) [mild, moderate, severe]
- Name of underlying disease (i.e., primary disease of nerve damage that cause neuropathic pain) [by disease name]
- Hepatic impairment [no, yes (mild, moderate, severe)]
- Renal impairment [no, yes (mild, moderate, severe)]
- Hemodialysis [no, yes]
- Creatinine clearance (continuous data)
- Creatinine clearance category [<15 mL/min, ≥ 15 to <30 mL/min, ≥ 30 to <60 mL/min, ≥ 60 mL/min]
- Past medical history [no, yes]
- Complications [no, yes]
- Past medical history or complications of cardiovascular disorder^a [no, yes]
- Past medical history of angioedema^b [no, yes]
- Past medical history or complications (at the start of treatment): Peripheral edema and edema-related events^c [no, yes]
- Past medical history or complications (at the start of treatment): Dizziness, somnolence, loss of consciousness, syncope, and potential for accidental injury^c [no, yes]
- Past medical history or complications (at the start of treatment): Vision-related events^c [no, yes]
- Concomitant medications (at the start of treatment) [no, yes]
- Concomitant use of analgesics^d (at the start of treatment) [no, yes]

^a: Past medical history or complications coded to the MedDRA SOC “Cardiac disorders” or “Vascular disorders”

^b: Past medical history coded to the MedDRA HLT “angioedemas”

^c: The same definition as the major investigation items

^d: The following analgesics will be considered as candidates and identified: drugs classified as “3 digits, 114 antipyretics, analgesics, and anti-inflammatory agents; 3 digits, 113 antiepileptics” in the drug name data file or drugs classified as “Standardised Drug Groupings (SDG), analgesia producing opioids; ATC 3rd level, N06A (ANTIDEPRESSANTS)” in the WHO-drug dictionary.

- Concomitant use of opioid analgesics^a (at the start of treatment) [no, yes]
- Concomitant use of oxycodone or lorazepam^b (at the start of treatment) [no, yes]
- Concomitant use of drugs causing angioedema^c (at the start of treatment) [no, yes]
- Concomitant use of thiazolidines^d (at the start of treatment) [no, yes]

• Information on administration of Lyrica

The following information on administration of Lyrica will be tabulated in the safety analysis set.

- Duration of administration [\leq 4 weeks, $>$ 4 to \leq 13 weeks, $>$ 13 weeks]
- Timing of administration (at the start of treatment) [morning, noon, evening, bedtime, other]
- Timing of drug administration (at the start of treatment) [before meal, after meal, other]
- Daily dose (continuous data)
- Daily dose (at the start of treatment) [\leq 25 mg, $>$ 25 to \leq 75 mg, $>$ 75 to \leq 150 mg, $>$ 150 to \leq 300 mg, $>$ 300 to \leq 600 mg, $>$ 600 mg]
- Daily dose (maximum) [\leq 25 mg, $>$ 25 to \leq 75 mg, $>$ 75 to \leq 150 mg, $>$ 150 to \leq 300 mg, $>$ 300 to \leq 600 mg, $>$ 600 mg]
- Daily dose (final) [\leq 25 mg, $>$ 25 to \leq 75 mg, $>$ 75 to \leq 150 mg, $>$ 150 to \leq 300 mg, $>$ 300 to \leq 600 mg, $>$ 600 mg]

Dosing period is from the day of initial dose in the survey to the day of last dose, including period of dose interruption. Daily dose (continuous data) will be calculated as the mean dosage during the entire period in which Lyrica was actually administered to each patient excluding pro re nata (PRN) prescription, and the mean, standard deviation, and mode will be calculated in the safety analysis set.

^a: The following opioid analgesics will be considered as candidates and identified: drugs classified as “Standardised Drug Groupings (SDG), analgesia producing opioids” in the WHO-drug dictionary.

^b: Drugs classified as “7 digits, 8119002 oxycodone hydrochloride hydrate or 1124022 lorazepam” in the drug name data file

^c: The following drugs causing angioedema will be considered as candidates and identified: drugs classified as “4 digits, 6111 penicillins; 3 digits, 254 contraceptives” in the drug name data file or drugs classified as “Standardised Drug Groupings (SDG), non-steroidal anti-inflammatory drugs (NSAIDs); ACT 3rd level, C09A (ACE INHIBITORS, PLAIN), C09B (ACE INHIBITORS, COMBINATIONS), C09C (ANGIOTENSIN II ANTAGONISTS, PLAIN), C09D (ANGIOTENSIN II ANTAGONISTS, COMBINATIONS); ACT 3rd level, B01AD (Enzymes)” in the WHO-drug dictionary.

^d: Drugs with non-proprietary name of pioglitazone in the drug name data file

